Cold Pressor Test (CPT): Measures of pain sensitivity will be obtained using the CPT, a procedure that has been used widely in laboratory studies to measure pain perception and tolerance,⁷⁰ as well as self-report measures of pain severity and disability and exercise motivation (Appendix 1). The cold pressor protocol will follow guidelines from a previously published study investigating similar variables.⁷⁰ Chronic pain mentor [name], who has experience administering the cold pressor test, will provide supervision. Participants will be instructed to hold their right hand in temperature-controlled ice water, inside a cold pressor apparatus, up to their wrist and to keep the hand still. They will be instructed to say when they first experience pain and will be told to withdraw their hand when the pain becomes intolerable. Therefore two measures of pain sensitivity will be derived: "pain threshold" and "pain tolerance". Pain threshold is defined as the number of seconds between hand immersion in the ice water and the first report of "pain." Pain tolerance is defined as the number of seconds between hand immersion and hand withdrawal from the water. A maximum seven-minute time limit for immersion, unknown to the patient, will be imposed. The CPT will be obtained: A) in relation to the acute maximum load exercise assessment (pre- and post-CPX), and B) in relation to progressive exercise training (before, at mid-point, and after completion).

A) Participants will perform baseline pain ratings and the CPT in the late morning **one to five days before** each CPX, two and a half hours after IV placement and the breakfast of power bars provided. Blood will be sampled from the IV for ALLO+PA measurement just prior to the pain ratings and CPT. Participants will have fasted since midnight, as per procedures for the CPX. The post-CPX pain ratings and CPT will be performed on the day of the CPX, immediately after the 30' post-CPX blood drawing for ALLO+PA. Obtaining the baseline and post-CPX pain assessments at the same time of day on two separate days will control for potential effects of diurnal variation on pain sensitivity, as well as ALLO+PA levels.

B) The procedures in A will be completed before and after completion of the chronic exercise training program.

C) In addition, the baseline pain ratings and CPT procedures in A will be performed at the mid-point of the progressive exercise training program.

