Aim 1 : Hypothesis one will be evaluated by conditional LGMs. The Intercept of the LGM will be centered on the self report data from the baseline CPX assessment (i.e., first Slope loading will be fixed to 0.0). The intermittent time point (midpoint self-report session) will be freely estimated and the final time point (i.e the self-report data from the 13 week MAX-EX test session) will have a corresponding Slope factor loading fixed to 1.0. Accordingly, the mean and variance of the Slope factor will convey the fixed (average) and random effects (individual differences) of change for the time interval of interest. The two study groups will be dummy coded (using chronic pain/PTSD as the reference condition in the initial models) and included as predictors in the LGM to account for individual differences in symptom reduction (i.e. pain intensity, pain tolerance and threshold, depression and PTSD symptoms) due to treatment assignment. The Intercept will be regressed onto the treatment covariates to examine any pre-exercise training differences among treatment conditions. Moreover, individual differences in pre-treatment functioning will be held constant by regressing the Slope onto the Intercept. Hypotheses 1 will be supported in part by the statistical significance of the study group (dummy code) > Slope paths. In fact, these paths reflect study group x Time interaction effects. The nature of these interaction effects in the LGMs will be characterized using the procedures described by Curran, Bauer, and Willoughby.⁷⁸ All outcome measures will be analyzed in this fashion.

Aims 2 & 3: At both exercise assessment time-points, change scores will be computed ALLO+PA and these will be correlated with pain tolerance and pain threshold scores using Pearson or Spearman correlations, as appropriate. For exploratory purposes, ALLO+PA will be used as predictor variables in a regression equation to predict pain outcome (tolerance, threshold and intensity).

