(2) Breathing mouthpiece: The breathing mouthpiece worn during exercise testing may be uncomfortable. In addition, saliva will tend to accumulate in the subject's mouth when the mouthpiece is in place. This may lead to drooling and will be uncomfortable until subjects have figured out how to swallow with the mouthpiece in place.

(3) Cold Pressor Test: While the experience of pain is an expected part of this procedure, participants will be informed during the consent process that there will be a time limit imposed (without full disclosure of the actual time limit—7 minutes) and are therefore not at risk of freezing or other related injuries to their hand.

(4) Exercise Testing:

- a). Men may need to have parts of their chest hair shaved in order to attach electrodes; this hair grows back over the next few weeks.
- b). Exercise assessments (clinical treadmill and cardiopulmonary exercise testing) all require people to apply themselves with great effort. Although encouragement and careful medical supervision will help to make these tests as agreeable as possible, some people might still find it unpleasant.
- c). Maximal exercise testing is generally associated with a 1 in 10,000 chance of a bad reaction (heart attack or dying). In unselected populations, which include persons referred for exercise testing because of cardiac symptoms, the risk of myocardial infarction or death from exercise testing is approximately 1 in 2500. Specifically, the risk of death has been estimated at <0.01%. In an asymptomatic patient population, selected to have no history, signs, or symptoms of coronary artery disease (as in this study), the risk of harm would be expected to be even lower. However, all those enrolled will have a physical exam immediately before to best insure they are stable and they will have a cardiologist or nurse supervising the performance of the stress test to be sure they are maximally safe and well cared for if any problems develop in accordance with routine VA patient care protocols.

- d). The exercise physiologist and Cardiologist/Nurse Practitioner completing the test will be ACLS certified (Advanced Cardiac Life Support). Performance of the testing in the VABHS, Jamaica Plain Clinical Studies Unit (CSU) will allow immediate access to a code cart and defibrillator. Tests will only be completed when the VABHS Code team is also immediately available.

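### If anyone reaches the seven-minute cold pressor limit, tolerance is right-censored at 420 s; the plan analyses it as exact, so the mean training gain is understated and the group contrast can shift either way

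*Combined protocol and SAP*

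**What the plan says.** The Cold Pressor Test section gives the definition "Pain tolerance is defined as the number of seconds between hand immersion and hand withdrawal from the water" and adds the limit: "A maximum seven-minute time limit for immersion, unknown to the patient, will be imposed". The Protection Against Risk section repeats the seven minutes as a safety measure, so that participants are "not at risk of freezing or other related injuries to their hand".

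Under Aim 1, the Data Analyses section uses conditional latent growth models to explain "individual differences in symptom reduction (i.e. pain intensity, pain tolerance and threshold, depression and PTSD symptoms) due to treatment assignment". It then states: "All outcome measures will be analyzed in this fashion". The test is described as follows: "Hypotheses 1 will be supported in part by the statistical significance of the study group (dummy code) > Slope paths". Baseline is handled in the same model: "individual differences in pre-treatment functioning will be held constant by regressing the Slope onto the Intercept".

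Under Aims 2 and 3, ALLO+PA change scores are related to tolerance and threshold scores "using Pearson or Spearman correlations, as appropriate". Tolerance is also an outcome in an exploratory regression.

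The documents do not say how a participant stopped at the limit is recorded or analysed. There is no censored or time-to-event model, no sensitivity analysis and no count of capped values. They also give no mean, SD or expected share at the limit for tolerance.

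**The concern.** A participant who is stopped has not withdrawn because the pain became intolerable. The definition therefore yields a lower bound, not a value. An ordinary growth model or regression treats 420 s as the value itself.

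The hypothesised direction makes this worse. Hypothesis 3b expects tolerance to rise with training, so the limit would bind more often at endpoint than at baseline. Someone capped at both visits records a change of zero whatever happened in between.

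What is at stake is the tolerance result in Aims 1 and 3. Specific Objectives says the pilot data will supply effect sizes for a future trial, so a shrunken estimate would be carried forward.

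**Working it through.** **Inputs from the documents.** The limit is 7 × 60 = 420 s, tolerance is in seconds, and about 25 completers are planned. The plan has no figure for the share capped, so there is none to reproduce. The sample-size statement (effect size .35, N = 25) is not tied to tolerance and is not at issue here.

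**Assumptions, not from the documents.** Log tolerance is normal with SD 1, with visit-to-visit correlation .7 and a true change of .68 SD of change. A paired effect of about .68 is what 25 participants detect with 90% power (two-sided 5%). The baseline share capped, p, is varied.

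**Mean change.**
- SD of change = √(2 × (1 − .7)) = .775, so the true change is .68 × .775 = .527 log units.
- With baseline mean 0, the limit sits at c = Φ⁻¹(1 − p).
- A capped normal score with mean μ has mean μΦ(c − μ) − φ(c − μ) + c[1 − Φ(c − μ)].
- For p = 20%, c = .842. The baseline mean is −.280 + .842 × .20 = −.112. The endpoint mean is .527 × .624 − .380 + .842 × .376 = .266. The observed change is .377, and 1 − .377/.527 = 28% is lost.

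| Capped at baseline | Capped at endpoint | Observed change (true .527) | Shrinkage |
|---|---|---|---|
| 0% | 0% | .527 | 0% |
| 5% | 13% | .481 | 9% |
| 10% | 23% | .444 | 16% |
| 20% | 38% | .377 | 28% |
| 30% | 50% | .317 | 40% |
| 40% | 61% | .261 | 50% |

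A smaller true gain of .35 baseline SD behaves the same way: observed gains are .33, .30, .26, .22 and .19 at 5, 10, 20, 30 and 40% capped. With no true change, the mean change stays at zero.

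**Group contrast.** Let both groups truly gain .35 SD.
- If 10% of the reference group and 30% of the other start at the limit, the observed gains are .30 and .22. That is a spurious difference of −.08. Swapping the shares gives +.08.
- Regressing observed change on observed baseline and group stands in for the plan's baseline adjustment (visit correlation .6). The group coefficient then moves from .301 without a cap to .216 with it, and from −.308 to −.222 when the shares are swapped.

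**Correlations.** Take a true correlation of .50 between ALLO+PA change and change in log tolerance. At 10, 20, 30 and 40% capped:
- Pearson is .46, .43, .40 and .36.
- Spearman is .45, .41, .38 and .35, against .48 with no cap.
- For tolerance level rather than change, Spearman is .48, .48, .47 and .45, against .485 with no cap.

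**Raw seconds.** In the same model with n = 24:
- Paired-test power on log change falls from .89 to about .86, .80, .74 and .67.
- On seconds it is .63 with no cap and about .80, .78, .74 and .68 with it.
- Pearson with change in seconds goes from .29 to .42, .42, .40 and .37.
- The limit trims a long right tail, so power and correlation rise even though the mean gain in seconds still shrinks.

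**Does a censored model repair it?** With a true gain of .35 SD, a censored-normal fit returned .35 to .36 at 10 to 40% capped. With n = 24 and 10 to 20% capped, it recovered about 98 to 105% of the true change.

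**The case against.** The strongest reply is that the defect may never occur. No document gives a tolerance distribution, so the share reaching seven minutes could be zero. That stands, and every size above depends on it.

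A reader might go further than the documents allow in four ways.

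- **Training effects are always biased toward zero.** This holds for the mean gain in tolerance. The group-to-slope path, which partly decides Hypothesis 1, can be moved in either direction.
- **Power and the ALLO+PA correlation are lost.** This holds on a log scale for change scores. The plan defines tolerance in seconds and names no transformation for these analyses. On seconds, the same simulation shows higher power and higher Pearson correlation with the cap than without it.
- **Spearman cannot help.** The Aims 2 and 3 text forms change scores for ALLO+PA but does not clearly say that tolerance is also a change score, although Hypotheses 3a and 3b speak of change. Ranking does not repair change scores. For tolerance levels it nearly does.
- **Tolerance is the main pain measure for Aim 3.** The plan does not rank it. Aim 3 also names self-reported ratings, and threshold is defined alongside tolerance.

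It can also be said that a censored growth model is demanding at about 25 completers in a proof-of-concept pilot. That is fair, and it is why a sensitivity analysis is an acceptable minimum.

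**Conclusion.** The point holds conditionally. If any participant is stopped at seven minutes, the stated analysis treats a lower bound as an exact value and understates the mean training gain in tolerance. Under the log-normal assumptions the understatement runs from about 9% at a 5% baseline share to about 50% at 40%; it is nil if nobody is capped. The group contrast on the slope is distorted, in a direction that cannot be predicted beforehand, if the groups differ in the share capped.

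Correlations with change in log tolerance are attenuated under both Pearson and Spearman. Spearman correlations with tolerance level are little affected. A loss of power is not established for the scale in seconds that the plan uses.

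Threshold is affected only if pain goes unreported for seven minutes. Self-reported pain, PTSD and depression outcomes are untouched.

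**What to change.** Leave the safety limit as it is and change only the analysis text.

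1. State that a test stopped at 420 s is recorded as right-censored, separately from voluntary withdrawal.
2. Report the number capped by session and study group, for tolerance and for threshold.
3. If any are capped, estimate change in log tolerance with a censored-normal (Tobit) mixed or growth model, at least as a prespecified sensitivity analysis beside the stated model. With no capped values it reduces to the ordinary normal model for log tolerance.
4. For Aim 3, say whether tolerance enters as a level or as a change. For change, model pre- and post-exercise tolerance jointly as censored outcomes with ALLO+PA change as predictor. Using capped pre-exercise tolerance as an exact covariate would repeat the error.

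The cost is analysis-plan wording and some extra modelling, with no new data. The censored model relies on a distributional form that cap counts do not verify, so residuals among uncensored values should be checked. Its estimates will also be less stable at about 25 completers.

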****For a timeline of Assessments please refer to Table 2 at the end of the protocol.**

*****Please note that if any abnormalities occur during the MAX-EX testing, the participants physician will be contacted and further testing may be recommended. If referred for further testing participants will need physician clearance prior to being able to continue in the study or may be terminated from their participation in the study.**

Chronic Exercise Rehabilitation Training Program

In an effort to design an effective and safe exercise program for a population with chronic pain and PTSD, we reviewed exercise studies in chronic pain, PTSD, heart failure, and cardiovascular disease populations, which may all share pathophysiological characteristics⁷. We determined that a "progressive" training method is likely to provide the most clinical benefit as well as reduce the risk of exercise related adverse events in this vulnerable population.⁸⁰⁻⁸¹ Specifically, we plan to prescribe a 12-week, moderate to vigorous intensity progressive aerobic exercise training regimen to ease sedentary trauma exposed controls as well as chronic pain and PTSD patients into exercise. We believe that this design will both maximize the clinical benefits of the intervention for most patients, as well as allow us to investigate relationships between exercise-induced changes in chronic pain and PTSD symptoms and changes in ALLO+PA physiology.

Progressive Exercise Training: According to Goodrich, Larkin, Lowery, Holleman and Richardson,⁷³ progressive exercise training can help to minimize the risk or occurrence of a range of exercise-related adverse medical events, particularly with the complex study population which will be starting at a sedentary level and therefore, may not be able to initially achieve the heart rate goals prescribed in standard exercise training protocols.

The exercise prescription will be individually designed and geared toward an intensity manageable by the individual. It will also be relatively easy to integrate into an individual's personal lifestyle. As an example, an individual will be instructed to wear a pedometer and heart rate monitor and progressively increase walking duration and intensity over each week. The devices will be programmed by the exercise physiologist and will allow the participant to walk at a frequency, intensity and duration in accordance with a target heart rate reserve range (HRR) defined by resting and peak heart rates established during baseline MAX_EX testing. The devices will record the activity performed by the participant and allow the exercise physiologist to adjust instruction accordingly when the participant returns to the clinic each week. This will minimize improper performance of the exercise prescription as well as exercise and non-exercise related adverse events. Along with close monitoring by study staff, (i.e. weekly telephone calls and check-ins as well as the end-point in person MAX_EX assessment), we believe that this method would feasibly, safely and effectively promote the progressive realization of potential biological benefits of the full exercise program. Ultimately, this method will start each participant at a level of intensity that matches their capability/ability level and progressively move them towards achieving the heart rate goal of $\geq 80\%$ of their HRR.

Summary of Approximate Weekly Telephone Calls:

The PI or other trained study staff will provide check-in telephone calls, based on the mutual agreement between participant and study staff, to each participant at week 4, when the participant is primarily exercising at home, and week 10, toward the end of the participant's exercise prescription. Assessments of exercise motivation will be made during these calls. Other data points with these measures will be gathered in person at baseline, midpoint, and endpoint sessions. There will also be "approximately weekly" check-in telephone calls for motivational enhancements without assessments for the purpose of helping the participant maintain compliance with their exercise prescription.. Just prior to each of the assessment based phone calls, the TTM exercise stage of change, self-efficacy, decisional balance and processes of change measures will be administered in order to determine which stage of the telephone script (see Appendix A) to intervene with, as well as which processes of change to highlight during the telephone intervention. Based on the TTM stage of change measure, if a person has not been exercising at all in the past six months and is not planning to at any point in the near future (within the next 6 months), the calls will start at the Pre-contemplation stage in order to help increase readiness for exercise initiation. If the person is contemplating exercising in the near future (at some point in the next 6 months), the calls will start at the Contemplation stage in order to increase readiness. If the person is ready to being exercising at some point within the next month, the calls will begin at the Preparation stage. If the person has begun exercising within the past month, the calls will begin at the Action stage. If the person has been exercising regularly for the past six months, the calls will begin with the Maintenance stage. Please note that we anticipate all participants will start the calls in the Action stage since they will have started their exercise prescription, however, we recognize that over-time, they may encounter real and/or perceived barriers to staying in the action stage and could likely revert to an earlier stage of change. Thus, the staging measure will be needed for the beginning of each call and the additional measures will let the telephone counselor know which processes of change, etc. to highlight during the implementation of the telephone script. The overall goal of the phone sessions are to help increase the participant's motivation to stay on track with their exercise prescription.

This proof-of-concept pilot study is among the first to investigate antinociceptive neurobiomarkers that may be implicated in comorbid chronic pain and PTSD. We think that the exercise training methodology to be employed will yield maximum results (i.e. increases in the capacity for both ALLO +PARElease and improvement in patient symptomatology and overall functioning). This

progressive exercise training method has been found to be efficient and is the standard prescription for most exercise training programs to date.⁸³ It is also in line with time-based activity pacing used in the rehabilitation of chronic pain populations to minimize disability and maximize activity over time. 74

Taking the above into account for this pilot study, we propose the following exercise prescription after baseline maximum load exercise assessment:

Progressive Exercise Program: Based on the “Active Physical Treatment Model”⁷⁵⁻⁷⁶ individuals with chronic pain are primarily sedentary and physically deconditioned and need a progressive approach to work up to standard exercise prescriptions as defined by the ACSM.

A. Exercise Prescription:

Weeks 1-2:

Warm-up: 5-10 minutes, light walking at 30-50% of HRR

Exercise: walking for 30 minutes at 40-60% of HRR (based on baseline MAX-EX test)

Cool-down: 5 minutes, gradual reduction in walking intensity to target HRR: 30-50%

Weeks 3-4:

Warm-up: 5-10 minutes, light walking at 30-50% of HRR

Exercise: walking for 30 minutes at 50-60% of HRR (based on baseline MAX-EX test)

Cool-down: 5 minutes, gradual reduction in walking intensity to target HRR: 30-50%

Weeks 5-6:

Warm-up: 5-10 minutes, light walking at 30-50% of HRR

Exercise: walking for 45 minutes at 60-70% of HRR (based on baseline MAX-EX test)

Cool-down: 5 minutes, gradual reduction in walking intensity to target HRR: 30-50%

Weeks 7-12:

Warm-up: 5-10 minutes, light walking at 30-50% of HRR

Exercise: walking/running for 45 minutes at 70-85% of HRR (based on baseline MAX-EX test)

Cool-down: 5 minutes, gradual reduction in walking intensity to target HRR: 30-50%

B. Exercise Implementation:

Baseline Initial MAX-EX test. **Weeks 1- 3:** Exercise 1x/week in clinic and 2x/week at home

**** Please note these exercise training sessions will be scheduled based on the mutual agreement between participant and study staff and are therefore subject to change.**

Weeks 4-12: Exercise 3x/week at home. Motivational telephone calls by psychologist at weeks 4 and 10. There will also be an approximate 1x/month check in with the exercise physiologist to allow actigraph data to be downloaded and a modification to the exercise prescription if indicated.

****Week 6:** The midpoint check in will consist of implementation of the cold pressor pain threshold test and self-report assessment measures in order to capture change in pain, mood, PTSD and exercise motivation outcome variables.

Week 13-15: Final MAX-EX test.

****Please note,** after completion of the study, two follow-up phone calls will be administered at 1-month and 6-months post-study. Please see the timeline of assessments for the questionnaires to be administered during these calls. Such follow-up will allow us to administer the necessary mood, pain, PTSD severity, exercise behavior and exercise motivation questionnaires to help determine if post-exercise intervention improvements have been sustained or help us to identify barriers for sustaining improvements made while in the active phase of the study.

Summary of Exercise Training Implementation: Upon completion of the initial MAX-EX and cold pressor test sessions, each participant will be instructed to return to VABHS for 2 exercise training sessions with our experienced exercise physiologist who will teach them how to conduct their exercise regimens. After these two sessions, the exercise physiologist will instruct the participants to gradually increase the frequency of their prescribed exercise sessions at home to 3x/week by week four. During weeks three and twelve, when the participant is primarily exercising at home, the PI or other appointed and trained research staff will call the participant in order to provide a brief check-in and to discuss any barriers to exercise the participant may be experiencing at home. The PI, who is trained in the identification of barriers to maintaining exercise compliance, will use basic motivational interviewing techniques (i.e. reflective listening) and problem solving strategies, (the current standard of care in this area), in order to facilitate exercise compliance while maintaining participant safety. (Data from this pilot study thus could guide future development of a standardized motivationally based exercise behavior change intervention aimed at promoting long-term exercise adherence in this population.) At weeks 13-15, participants will complete a final MAX-EX, pain ratings, and CPT to assess any changes in their psychological, neurobiological, and pain responses to chronic exercise.

To allow verification of the participant's exercise at home, the participant will wear an actigraph and heart rate monitor to measure overall activity and heart rate, respectively. During exercise, the pre-programmed heart rate monitor will "beep" when the participant needs to increase exercise intensity. Use of this device will ensure that participants are achieving the targeted heart rate range (HRR) in accordance with their individualized progressive prescriptions. This will ensure standardization of the exercise prescriptions and also minimize errors. Participants will be trained in the use of their device during initial exercise sessions in the clinic and will be instructed to call if problems arise. Data collected from the heart rate monitor will be downloaded when the participant returns to the clinic for their monthly check-ins during weeks 4-12 (when they are primarily exercising at home), as well as at the end-point maximum load exercise session. During the check-ins, participants will meet with the exercise physiologist in order to ensure understanding of the exercise prescription and how to perform it properly. The data from the devices will provide objective data to confirm whether the participant is complying with the exercise prescription. The data will also be used to support future funded studies aimed at refinement of individualized exercise prescriptions for chronic pain/PTSD patients, as well as the development of a motivationally-based exercise behavior change protocol tailored to this population that may serve to augment other treatments for pain and PTSD.

Finally, we recognize that throughout a more "chronic" exercise training program of 3 months, participants who are more recent alcohol or substance remitters may face challenges that could increase risk for relapse. Therefore, the PI will monitor participants for relapse risk during the initial and endpoint screening sessions, as well as during the weekly phone call sessions and interim visits to the clinic for exercise training. If the participant reports a lack of appropriate social support or exhibits high levels of acute distress related to craving, psychiatric diagnoses or environmental stressors, he/she will be referred to appropriate clinical care to help with sustainment of remission. The PI will continue consultation with providers in order to assess the efficacy of such interventions. If the participant relapses or continues to display significant levels of distress or risk for relapse such that continued participation in the protocol is contraindicated, the participant will be terminated from the study and referred for further evaluation and clinical care as appropriate.

Blood Drawing: We will draw 10 cc of blood at the screening session. We will draw 20 cc of blood before the CPT or MAX-EX sessions. At the MAX-EX testing sessions only, we will also draw 20 cc at the post MAX-EX (5 and 30 minute) blood drawings. We will draw 4 cc of blood at each step increase in exercise load during the MAX-EX. At the CPT sessions only, we will draw 10 cc of blood at the t post 45 minute CPT blood draw. Previous experiences shows that participants tolerate blood drawing at this level during exercise testing without difficulty. Therefore, a total of ~300-316 cc of blood will be drawn during the study which corresponds to a little more than half the amount of a standard blood donation.

